6.2.2 Non-responder Imputation Analysis

If assessment of vIGA-AD after baseline is missing, the subject will be considered as non-responder (for example, no vIGA-AD success in the analysis of vIGA-AD success). For the vIGA-AD success endpoints, subjects with missing baseline vIGA-AD score will be considered as non-responder for these endpoints only. That is, for the secondary efficacy endpoints of vIGA-AD score of clear (0) or almost clear (1) and vIGA-AD score of clear (0), the post-baseline assessment at a specific visit will be established based on the vIGA-AD score at that visit only, regardless of the availability of the baseline vIGA-AD score.

Similar imputation method will be used for 4-point reduction on the average weekly WI-NRS and EASI-75. For EASI-75, subjects with missing baseline EASI total score will be considered as non-responder. For 4-point reduction on the average weekly WI-NRS, subjects with missing baseline average weekly WI-NRS will not be imputed since the analysis of WI-NRS endpoints will be performed based on the WI-NRS population from which subjects with a missing baseline average weekly WI-NRS are excluded.

6.2.3 Tipping Point Analysis

As a sensitivity analysis to the multiple imputation analysis as described in Section 6.2.1 for the vIGA-AD success primary endpoint and secondary endpoint of vIGA-AD success among subjects with Moderate disease at baseline, a tipping point analysis will be performed in order to determine the inflection point at which the inference under the missing not at random (MNAR) assumption changes substantially.

The sensitivity analysis for the primary endpoint will be performed by using a specified sequence of shift parameters. The range of shift parameters to be included in this analysis are 0 to 2 by 0.2 for active and -2 to 0 by 0.2 for Vehicle. The values at which the results of the primary analysis are shifted from significant (i.e., $\alpha \le 0.05$) to non-significant (i.e., $\alpha > 0.05$) will be determined. Steps 1 and 3 of the analysis will be the same as for the multiple imputation analysis as described in Section 6.2.1. However, Step 2 of the analysis is where the shift parameters will be applied.

6.3 Interim Analysis

No interim analysis is planned for this study.

	STATISTICAL ANALYSIS PLAN, Version 1.0
Protocol Number: ARQ-151-312	Sponsor: Arcutis Biotherapeutics, Inc.

6.4 Multicenter Studies

The study will be conducted at approximately 60 study sites in the US, Canada, and Poland. During the conduct of the study, additional countries and/or sites may be added if necessary.

Sites with less than 16 subjects in the ITT population will be pooled within a country:

- a. Sites with less than 16 subjects will be ordered from lowest to highest in terms of number of ITT subjects. In case of ties, the ordering for tied sites will be determined according to the site identification number (from smallest to largest).
- b. Sites will be combined beginning at the smallest until the resulting pooled site contains at least 16 ITT subjects with at least 1 subject in each treatment group. The sites pooled in this way will be considered as a single site in the statistical analyses.
- c. The process described above will resume for the remaining sites not meeting the criterion of at least 16 ITT subjects with at least 1 subject in each treatment group. If the final set of pooled sites does not meet the criterion of at least 16 ITT subjects with at least 1 subject in each treatment group, the final set will be pooled with the preceding pooled site.
- d. If there is only one site with less than 16 ITT subjects with at least 1 subject in each treatment group, then this site will be combined with the site with the second lowest number of subjects. As above, in the case of ties, the ordering for tied sites will be determined according to the site identification number (from smallest to largest).

As a sensitivity analysis of different pooling strategy, sites that have randomized less than 50% of the number of randomized subjects at the site with the largest number of randomized subjects, those sites will be pooled within each country. The sensitivity analysis of pooling strategy will be applied for the primary endpoint only.

6.5 Multiple Comparisons/Multiplicity

To control for familywise type I error at level of 0.05, the secondary endpoint of vIGA-AD Success at Week 4 for subjects with vIGA-AD score of 'Moderate' at randomization will only be tested if the primary endpoint demonstrates statistical significance. In addition, the remaining secondary endpoints will be inferentially tested only if the primary and the secondary endpoint (vIGA-AD Success at Week 4 for subjects with vIGA-AD score of 'Moderate' at randomization) comparisons are statistically significant using hierarchical testing procedure by partitioning of alpha.

Upon successful demonstration of statistical significance for the primary and above secondary endpoint, the remaining endpoints will be grouped into secondary endpoint family 1, comprised of the 4-point reduction on the WI-NRS at Week 4, Week 2 and Week 1, and secondary endpoint family 2, comprised of the EASI-75 at Week 4, vIGA-AD of 'clear' or 'almost clear' at Week 4,

	STATISTICAL ANALYSIS PLAN, Version 1.0
Protocol Number: ARQ-151-312	Sponsor: Arcutis Biotherapeutics, Inc.

vIGA-AD of success at Week 2 and Week 1, vIGA-AD of 'clear' or 'almost clear' at Week 2 and Week 1. An alpha level of 0.03 will be used to test the endpoints in the secondary endpoint family 1 sequentially. An alpha level of 0.02 will be used to test the endpoints in secondary endpoint family 2 sequentially.

In addition to the partitioning of the overall 0.05 alpha into two families, the Fallback Method will be applied. The fallback method is a modification of the fixed-sequence method, providing opportunity to test an endpoint later in the sequence even if an endpoint tested early in the sequence has failed to show statistical significance. The order of the endpoints remains important. The appeal of the fallback method is that if an endpoint later in the sequence has a robust treatment effect while the preceding endpoint is unsuccessful, there is a modest amount of alpha retained as a fallback to allow interpretation of that endpoint without inflating the Type I error rate. Applying the fallback method begins by dividing the total alpha (not necessarily equally) among the endpoints and maintains a fixed sequence for the testing. In this study, the Fallback Method will be applied to the fixed sequence of testing Family 1, and then Family 2.

As the testing sequence progresses, a successful test preserves its assigned alpha as "saved" ("unused" or "accumulated") alpha that is passed along to the next test in the sequence, as is the case for the sequential method. This accumulated alpha is added to the prospectively assigned alpha (if any) of that next endpoint and the summed alpha is used for testing that endpoint. Thus, as sequential tests are successful, the alpha accumulates for the endpoints later in the sequence; these endpoints are then tested with progressively larger alphas.

[figure not shown]
In this study, the Fallback Method will be applied following this sequence:

Family 1: Testing will proceed at the 0.03 level sequentially within Family 1. Should all 3 endpoints in Family 1 be statistically significant at the 0.03 level, then the full 0.03 alpha will be carried to Family 2. Family 2 would then be tested at the full (α =0.02+0.03=0.05).

Should, anywhere during the sequential testing of Family 1, there is a p-value >0.03, the testing within Family 1 will stop, and no additional alpha can be carried over to Family 2.

	STATISTICAL ANALYSIS PLAN, Version 1.0
Protocol Number: ARQ-151-312	Sponsor: Arcutis Biotherapeutics, Inc.

Figure 2 Multiple Testing Scheme

Achievement of vIGA-AD success is a score of "clear" or "almost clear" plus a 2-grade improvement from baseline.

WI-WRS Success is a 4-point reduction in WI-NRS among subjects ≥12 years old with WI-NRS ≥ 4 at baseline.

EASI-75: achievement of at least a 75% reduction in the Eczema Area and Severity Index

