5.7 Statistical Tests

Unless otherwise specified, all statistical tests will be two-sided and will be performed with a significant level of 0.05. Confidence intervals (CIs) will be two-sided with 95% coverage.

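### The one-way fallback in SAP 6.5 is valid but leaves part of the 0.05 unused: Family 2's 0.02 never returns to Family 1 (an optional improvement, not an error)

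*SAP*

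**What the plan says.** The stated aim in SAP 6.5 is "To control for familywise type I error at level of 0.05". SAP 5.7 makes the tests two-sided: "all statistical tests will be two-sided and will be performed with a significant level of 0.05". The two families open only after the primary endpoint and the vIGA-AD Moderate endpoint are both significant: "Upon successful demonstration of statistical significance for the primary and above secondary endpoint, the remaining endpoints will be grouped into secondary endpoint family 1", with Family 2 alongside it.

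- **Family 1** has three WI-NRS responder endpoints, at Weeks 4, 2 and 1: "Testing will proceed at the 0.03 level sequentially within Family 1".
- **Family 2** has EASI-75 at Week 4 and five vIGA-AD endpoints at Weeks 4, 2 and 1: "An alpha level of 0.02 will be used to test the endpoints in secondary endpoint family 2 sequentially".
- **Direction:** "In this study, the Fallback Method will be applied to the fixed sequence of testing Family 1, and then Family 2".
- **Forward transfer:** "Should all 3 endpoints in Family 1 be statistically significant at the 0.03 level", the 0.03 is carried on, and "Family 2 would then be tested at the full (α =0.02+0.03=0.05").
- **Stop rule:** at the first Family 1 p-value above 0.03, Family 1 ends and Family 2 receives nothing extra.

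Section 12.2 repeats 0.03 for Family 1 and 0.02 for Family 2. The summary table in Section 12.5 lists Family 1 at 0.03 only and Family 2 at 0.02 or 0.05. No section describes a return of alpha from Family 2 to Family 1. Figure 2, the testing scheme, could not be read, so this account rests on the text and the summary table.

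**The concern.** Suppose an itch endpoint gives a p-value between 0.03 and 0.05, and Family 1 stops there. Suppose all six Family 2 endpoints are then significant at 0.02. The 0.02 spent on Family 2 has been recovered in full, as the 0.03 would have been in the opposite case, but the SAP gives it nowhere to go. The itch endpoint is reported as not significant, although a rule with the same familywise bound could have allowed the claim.

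The pattern is foreseeable. The WI-NRS population (SAP 4.6) is limited to subjects aged 12 or older with a baseline weekly mean of at least 4 and at least 4 of 7 diary days. Family 2 uses the full ITT population. Family 1 therefore has the smaller sample. What is at stake is a secondary itch claim. The primary and vIGA-AD Moderate conclusions are settled before either family is opened.

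**Working it through.** **1. The plan's own figure.** 0.02 + 0.03 = 0.05 for Family 2 after three Family 1 successes. This reproduces exactly.

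**2. Familywise error with a return rule.** Compare the SAP's rule with one that retests Family 1 at 0.03 + 0.02 = 0.05 once all six Family 2 endpoints are significant at 0.02.

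- True nulls in both families: until a false rejection occurs, neither family can be fully rejected, so no alpha has moved. The first true null in each chain is tested at 0.03 and 0.02, and the total is at most 0.05.
- True nulls in one family only: the first true null there is tested at no more than 0.05.
- A true null at the primary or vIGA-AD Moderate step: any later rejection requires a false rejection at that step, at 0.05.

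So the bound is 0.05 with or without the return. A simulation agrees (nine correlated normal statistics, 400,000 runs per scenario; within/between-family correlations 0/0, 0.5/0.3 and 0.8/0.6):

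| Truth | One-way | With return |
|---|---|---|
| All nine null | 0.046 to 0.050 | 0.046 to 0.050 |
| Family 2 null, Family 1 real | 0.050 | 0.050 |
| Family 1 null, Family 2 real | 0.030 | 0.050 to 0.051 |
| Only the Week 1 itch endpoint null | 0.030 | 0.050 |

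Values just above 0.050 are simulation noise. The unused 0.02 appears in the last two rows. The return rule lost no rejection in any power run.

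**3. Gain for one itch endpoint if Family 2 is certain to succeed.** The two-sided critical values are 2.170 at 0.03 and 1.960 at 0.05, a difference of 0.210. With power P at 0.03, power at 0.05 is Φ(z_P + 0.210), ignoring the far tail:

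- 50%: Φ(0 + 0.210) = 58.3%
- 70%: Φ(0.524 + 0.210) = 76.9%
- 80%: Φ(0.842 + 0.210) = 85.4%
- 90%: Φ(1.282 + 0.210) = 93.2%

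The largest single-test gain is 8.4 points, at about 46% power.

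**4. Unconditional gain.** The documents give no effect sizes for itch or for Family 2, so the powers below are assumptions (marginal, at two-sided 0.05). Ranges run over the three endpoints and the three correlation settings, and gains accumulate down the sequence.

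| Assumed power | Gain per Family 1 endpoint (points) |
|---|---|
| All nine at 80% | 0.6 to 2.6 |
| All nine at 90% | 1.3 to 3.0 |
| All nine at 95% | 1.0 to 3.6 |
| Family 1 at 90/80/60%, Family 2 at 60 to 97% | 0.4 to 2.9 |
| Family 1 at 80/70/50%, Family 2 at 99% each | 5.5 to 8.7 |
| Family 1 at 70% each, Family 2 certain | 7.6 to 10.2 |

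A second check took one itch endpoint, with each Family 2 endpoint at 80 to 95% power at 0.02. The gain was 1.4 to 4.1 points if the itch test has 80% power at 0.03, 0.7 to 2.4 at 90%, and 2.2 to 7.7 at 50%. A weak itch test is thus the one case with larger gains before Family 2 is close to certain.

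**The case against.** The strongest reply is that nothing here is wrong. The SAP sets out to hold the familywise error at 0.05 and does so. It names its method, defines it as passing alpha forward along a fixed sequence, states the order, and gives the same levels in 6.5, 12.2 and 12.5. A return rule is a different procedure, and choosing not to use one is a legitimate preference. All of that stands.

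Three stronger readings are tempting, and the documents do not support them.

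- **That the one-way rule has no error-rate benefit at all.** This is true only of the 0.05 bound. When Family 2 effects are real and Family 1 is null, the one-way rule holds the itch error at 0.03 and the return rule lets it reach 0.05. A sponsor might want the stricter itch standard, although the SAP does not give that as a reason.
- **That any itch p-value between 0.03 and 0.05 is a lost claim.** The return applies only if all six Family 2 endpoints succeed at 0.02, including two at Week 1, and every earlier itch test in the sequence is at or below 0.05.
- **That the gain is 5 to 8 points at 50 to 80% power.** Those figures assume Family 2 success is certain, or independent of itch and already achieved. The unconditional gain is usually smaller. If the endpoints are correlated, the conditional powers also shift: with correlations 0.5/0.3 and Family 2 at 90% each, an itch test with 80% power at 0.03 has about 86% at 0.03 and 90% at 0.05, given six wins.

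**Conclusion.** The point holds as a free improvement. The SAP's fallback is valid and internally consistent but does not exhaust its alpha. Returning Family 2's 0.02 after six successes meets the same 0.05 criterion, takes nothing from any other test and can only add itch rejections. The price is a Family 1 error of up to 0.05 instead of 0.03 when all Family 2 effects are real.

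The size is modest: about 0.4 to 4 points of power per itch endpoint in most assumed scenarios, and about 5 to 10 points mainly when Family 2 is near-certain. These ranges rest on assumed powers and correlations and on normal approximations. The familywise result does not depend on them. The improvement is optional.

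**What to change.** Make the change before unblinding; after that, leave the rule as it stands.

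1. SAP 6.5, add: *If Family 1 stops and all six Family 2 endpoints are significant at 0.02, the 0.02 is carried back and Family 1 is retested in the same order at 0.05.*
2. SAP 6.5, stop rule: make the end of Family 1 testing subject to that sentence.
3. SAP 12.2, text and Family 1 heading: change the level to 0.03 or 0.05.
4. SAP 12.5 summary table: the same change for Family 1.
5. Figure 2: check it and align it with the text.

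All five belong together. Adding only the first sentence would contradict the stop rule and the 0.03 levels elsewhere, a conflict the SAP does not now have. The cost is a few lines of text and one extra programmed step, with no change to data collection, sample size or any other test.

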6.6 Examination of Subgroups

Subset analysis for the following subgroups will be performed for the primary and secondary efficacy endpoints:

- Age group (6 11 years vs. 12 17 years vs. ≥18 years),
- Gender (male vs. female),
- Race (White vs. Black or African American vs. Asian vs. other),
- Ethnicity (Hispanic vs. Non-Hispanic),
- Randomized vIGA-AD score (mild (2) vs. moderate (3)),

	STATISTICAL ANALYSIS PLAN, Version 1.0
Protocol Number: ARQ-151-312	Sponsor: Arcutis Biotherapeutics, Inc.

- Actual baseline vIGA-AD score (mild (2) vs. moderate (3)),
- Baseline % BSA (<10% vs. $\ge 10\%$),
- %BSA categories based on tertiles,
- Baseline EASI total score ($\leq 7 \text{ vs} > 7$),
- Baseline EASI total score based on tertiles
- Fitzpatrick skin type at Screening (Type I, II and III vs. Type IV, V, and VI),
- Prior inadequate response, intolerance, or contraindication to Topical Corticosteroids (yes vs. no),
- Facial Involvement (yes vs. no)

For subgroup based on tertiles, tertiles will be derived using pooled data from both treatment group based on the ITT population.

Details on these analyses are described in Section 12.4.

7 STUDY SUBJECTS

7.1 Disposition of Subjects

All subjects who provide informed consent will be accounted for in this study. The number of subjects who were screened and who failed screening (screen failures) will be presented. The reasons for screen failure will be presented for all screened subjects who failed screening.

The number of subjects randomized will be presented by treatment group. The number and percentage of the subjects included in each analysis population will be provided by treatment group. The number and percentage of the subjects who completed the study, who discontinued the study, the reasons for study discontinuation, and early termination due to COVID-19 disruption will be presented by treatment group. The percentages will be calculated using the number of the randomized subjects as denominator.

Number of days in the study will be summarized with descriptive statistics by treatment group and overall. For each subject, the number of days in the study will be calculated as following:

Number of days in study = Date of completion/discontinuation -1^{st} dose date +1

	STATISTICAL ANALYSIS PLAN, Version 1.0
Protocol Number: ARQ-151-312	Sponsor: Arcutis Biotherapeutics, Inc.

A listing of subject's disposition and randomization will be provided. Information on first screening for subjects who were rescreened, including the rescreened subject identifier and the reason for first screening failure, will be presented under the first screening subject identifier. The reason for screening failure will be listed as well.

A table of randomized strata vs. actual strata will be provided if there is any mis-randomization discrepancy.

7.2 Protocol Deviations

A data review will be conducted before database lock by the Medical Monitor and the Sponsor to classify protocol deviations as minor or major.

The number and percentage of subjects with at least one important protocol deviation (including important protocol deviations associated with COVID-19) will be summarized by deviation category and treatment group using the safety analysis set.

A listing of all protocol deviations will also be provided. The protocol deviations associated with COVID-19 and major PDs will be flagged.

8 DEMOGRAPHIC AND OTHER BASELINE CHARACTERISTICS

Demographics and baseline characteristics will be summarized with descriptive statistics using the ITT and safety population. The list of demographics and baseline characteristics to be summarized will include:

- Age (years)
- Age Group: 6-11, 12-17, 6-17 and \ge 18, 18-64 and \ge 65
- Child bearing potential
- Sex at birth
- Ethnicity
- Race*
- Baseline Height (cm)
- Baseline Weight (kg)
- Baseline Body Mass Index (BMI) (kg/m²): Adult, Child/Adolescent
- Fitzpatrick Skin Type

	STATISTICAL ANALYSIS PLAN, Version 1.0
Protocol Number: ARQ-151-312	Sponsor: Arcutis Biotherapeutics, Inc.

- Prior failure of Topical Corticosteroids, Topical Calcineurin Inhibitors, Eucrisa
- Atopic Dermatitis involvement on the face, on the eyelids
- Baseline vIGA-AD
- Average weekly baseline WI-NRS
- Daily baseline WI-NRS
- Baseline BSA (%)
- Baseline BSA (%) Group <10% and $\ge 10\%$, tertile groups
- Baseline EASI total score
- Baseline EASI score group \leq 7 and \geq 7, tertile groups
- Baseline SCORAD
- Baseline DLQI/CDLQI
- Baseline DFI
- Baseline POEM
- Baseline PHQ-8
- Baseline PHQ-A
- Baseline CDI-2

Adult: BMI $(kg/m^2) = (weight in kg)/[(height in cm/100)^2]$. Baseline height will be used to derive BMI for each visit since height is not collected at all visits.

Child and Adolescent (6 to 17 years): After BMI is calculated using the same formula above for children and teens, it is expressed as a percentile obtained from either a graph or a percentile calculator. Percentiles will be calculated using data files and instructions provided by the CDC (https://www.cdc.gov/growthcharts/percentile data files.htm). Baseline height will be used to derive BMI for each visit since height is not collected at all visits.

A listing of all demographics, analysis population flag, reason not included in the efficacy analysis will be provided.

^{*}Subjects who reported more than one race will be summarized as 'Multiple' races in the table. All races selected will be displayed in the listing.

	STATISTICAL ANALYSIS PLAN, Version 1.0
Protocol Number: ARQ-151-312	Sponsor: Arcutis Biotherapeutics, Inc.

9 SURGICAL AND MEDICAL HISTORY

Surgical and medical history will be coded according to the Medical Dictionary for Regulatory Activities (MedDRA), Version 23.0 or higher.

Surgical and medical history will be summarized by system organ class (SOC) and preferred term (PT) using the safety analysis set. A subject who experienced the same surgical and medical history event multiple times will be counted only once for the corresponding PT. Similarly, if a subject experienced multiple surgical and medical history events within the same SOC, the subject will be counted only once for that SOC. Surgical and medical history events will be sorted alphabetically by SOC and within each SOC the PT will be presented by descending frequency in the safety analysis set.

10 PRIOR AND CONCOMITANT MEDICATIONS

Medications will be coded according to the World Health Organization Drug Dictionary (WHO-DD) B3 September 2020.

Prior medications are defined as any medication started and discontinued prior to the first study treatment dosing. Concomitant medications are defined as any medication taken after the first study treatment dosing, including those who started prior to the first study treatment date and continued past that date. See Appendix 2 for handling of completely or partially missing dates for prior and concomitant medications.

Incidence of prior and concomitant medications will be tabulated by ATC level 3 and PT using the safety analysis set. A subject with the same medication taken multiple times will be counted only once for the corresponding PT. Similarly, if a subject has taken more than one medication within the same ATC level, then the subject will be counted only once for that ATC. Prior and concomitant medications will be sorted alphabetically by ATC level and within each ATC level, the PT will be presented by descending order.

